### *Analysis of LA Fibrosis Progression*

The primary outcome variable will be changes in the percentage of fibrosis from baseline, 3- and 12-months via CMR assessments in patients randomized to receive dronedarone vs. placebo.

We will apply models for longitudinal data to analyze the LA fibrosis progression over the follow-up period. The two most popular approaches for longitudinal data are the Linear Mixed-effects Model approach (LMM) and Generalized Estimating Equations (GEE). The LMM requires parametric assumption such as, normality on the random effects and model errors, and it is more powerful when the assumptions are met, but vulnerable to departures from the assumed distributions. GEE provides robust

estimates because it does not require any distribution assumption. Therefore, we will first investigate the distribution of the outcome, and if the distribution assumption is reasonable, we will use LMM model, otherwise, we will use GEE approach. Due to the clustering effect at a physician level, we will use random effects in LMM or working correlation in GEE model to account for the correlations. In all the models, the primary predictor is the intervention condition. We will also consider controlling other potential confounders if the data exhibits any. The intervention effect is assessed by the estimated coefficient of the primary predictor. The coefficient with right direction and a p value  $<0.05$  indicates there is a significant intervention effect.

Per standard principles, the primary analyses will be done on an intention to treat basis (ITT), treating all randomized patients with available outcome data regardless of compliance. A Robustness Analysis will include a per protocol analysis, where only those patients who actually received their assigned treatment (e.g., those who received dronedarone per the dosing protocol) will be analyzed. In terms of missing data, the survival analysis approach to the AF recurrence outcome will censor any patients who drop out of the study without AF recurrence at the time of their last known contact. While we would propose such patients to have their first documented recurrence date counted as their failure date, alternative analysis approaches for the analysis of interval-censored data will also be considered for robustness.

For LA fibrosis regression, the missing data will be considered in the analysis. In the LMM model under ‘missing at random’, the factors associated with the missing values will be examined and then included to account for the missing values. As for the GEE approach, the likelihood of being observed for patients will be estimated and incorporated into the model to achieve unbiased estimates. Sensitivity analysis by multiple imputation will be conducted to assess how the missing data will impact the results. Patients will be considered lost to follow-up for the primary endpoint of fibrosis progression if they fail to attend any of the CMR visits.

The study is defined as positive if the analyses yield the coefficients of the intervention for both co-primary endpoints with a right direction and a p-value  $<0.05$ .

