#### **2) Progression of left atrial fibrosis**

Monitoring will start at the baseline CMR scan prior to ablation and up to the end of the clinical trial.

Defined as:

- a) The percentage (%) of new fibrosis seen on the 12-month CMR scan compared to CMR scans taken at baseline and at 3-months post-ablation.

The primary endpoints will be compared between the treatment (dronedarone) and control arms (placebo) respectively.

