### ***Twelve-month CMR to assess for new fibrosis formation***

After segmentation and measurement of LA fibrosis on pre-ablation scans and on 3-month post-ablation scans, we will use the latter as baseline for our trial to see if any new enhancement has formed or regressed (Figure 3). Transient post-ablation lesions will be defined as enhancements detected on the first post-ablation scan but not in the second post-ablation scan. New fibrosis will be defined as enhancement detected on the second post-ablation scan and absent on the first post-ablation scan. Both of these parameters will be reported as the percentage of total LA area.

**Figure 3:** There is new enhancement detected on the post-ablation MRI of the left atrium. New fibrosis is displayed in green. The red area represents ablated regions. Adapted from Kheirkhahan et al.

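### The fibrosis co-primary is defined and powered as one 12-month value, but success rests on a longitudinal-model coefficient with no 12-month contrast named, and the reference scan differs between sections

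*Combined protocol and SAP*

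**What the plan says.** All sections cited are in the combined protocol and SAP.

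- **Endpoint.** *Primary Endpoints, 2) Progression of left atrial fibrosis* takes the percentage of "new fibrosis seen on the 12-month CMR scan compared to CMR scans taken at baseline and at 3-months post-ablation". *Twelve-month CMR to assess for new fibrosis formation* makes this operational: "New fibrosis will be defined as enhancement detected on the second post-ablation scan and absent on the first post-ablation scan". Both give one number per patient.
- **Sample size.** *Sample Size Estimation, Atrial Fibrosis Progression* also works with one number per patient: control mean 10%, SD 1.59, a 20% reduction, and more than 99% power with 86 randomised patients and 20% dropout.
- **Analysis.** *Analysis of LA Fibrosis Progression* says "The primary outcome variable will be changes in the percentage of fibrosis from baseline, 3- and 12-months via CMR assessments", then "We will apply models for longitudinal data to analyze the LA fibrosis progression over the follow-up period". The model is a mixed model, or GEE if the distributional assumptions look doubtful, with physician clustering. The test is set by "The intervention effect is assessed by the estimated coefficient of the primary predictor", the predictor being treatment arm. The success rule follows: "The study is defined as positive if the analyses yield the coefficients of the intervention for both co-primary endpoints", each in the right direction with p below 0.05.
- **Reference scan.** The endpoint definition names baseline and 3 months. *CMR Protocol* compares the follow-up scans with baseline. The *Twelve-month CMR* section, speaking of the 3-month scan, says "we will use the latter as baseline for our trial to see if any new enhancement has formed or regressed".
- **Units.** Baseline fibrosis is a percentage of the atrial wall by volume (*Baseline CMR*). New fibrosis is a percentage of LA area (*Twelve-month CMR*).
- **Covariates.** *Stratification, Randomization and Blinding* plans adjustment for Utah stage. *General Considerations for Data Analysis* adds whatever proves imbalanced, and *Analysis of LA Fibrosis Progression* will consider confounders if the data show any.

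**The concern.** The definition and the decisive test do not clearly refer to the same quantity. Under the *Twelve-month CMR* definition, new fibrosis has no 3-month value, because the 3-month scan is the reference. A longitudinal model of changes at several visits therefore needs some other variable, and the plan does not name it. If arm is the only treatment term in a repeated-measures model, its coefficient is an average over the modelled visits and not the 12-month difference.

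The choice of visit is not cosmetic. *Three-month CMR to visualize ablation-induced scars* uses the 3-month scan to read ablation lesions, and patients are randomised after the ablation. A change from the pre-ablation scan to 3 months would carry procedural scar that treatment had no part in creating. The reference scan decides whether that scar enters the outcome.

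Both co-primaries must succeed, so this coefficient is half of the trial's decision rule. Two analysts could follow the text in good faith and report different effects from the same scans.

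**Working it through.** **Step 1. Reproduce the plan's power.** Inputs from *Sample Size Estimation*: difference = 20% × 10 = 2.0 points, SD 1.59, two-sided alpha 0.05, 1:1 allocation, 20% dropout.

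- 86 × 0.8 = 68.8 evaluable, taken as 34 per arm.
- Difference / (SD × √(2/n)) = 2.0 / (1.59 × √(2/34)) = 5.19. Power = Φ(5.19 − 1.96) = 0.9994, or 0.9992 with the noncentral t.
- With 330 randomised, 165 × 0.8 = 132 per arm, and power is about 100%.

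Both stated figures reproduce, using one value per patient.

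**Step 2. What a single arm coefficient estimates.** With complete data, exchangeable correlation and no arm-by-visit term, the arm coefficient is the simple average of the visit-specific differences. Let e3 be the 3-month effect. The documents do not give it, so it is an assumption shown as a range. Treatment starts on the day of ablation (*Dosing and IMP Administration*), so e3 need not be zero. The 12-month effect is 2.0.

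- 3- and 12-month changes as responses: (e3 + 2.0)/2.
- All three scans as responses, with no arm difference expected at baseline: (0 + e3 + 2.0)/3. This is the weaker reading, because the text speaks of changes.

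| Assumed e3 | 12-month contrast | Average of two changes | Average of three scans |
|---|---|---|---|
| 0 | 2.0 | 1.0 | 0.67 |
| 0.5 | 2.0 | 1.25 | 0.83 |
| 1.0 | 2.0 | 1.5 | 1.0 |
| 2.0 | 2.0 | 2.0 | 1.33 |

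For the two-change reading the gap runs from half the effect to none. If one 12-month value per patient is modelled with physician clustering, the coefficient is the 12-month difference and there is no gap.

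**Step 3. Compare with sampling error.** The 95% half-width for the 12-month difference at 132 per arm is 1.969 × 1.59 × √(2/132) = 0.385. A target of 1.0 in place of 2.0 is well outside that.

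**Step 4. Does power suffer?** Assume that SD 1.59 also applies to the 3-month change (the plan gives it only for progression), and let ρ be the assumed correlation between visits.

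- Two-change average, worst case e3 = 0: effect 1.0, SD 1.59 × √((1+ρ)/2), 132 per arm. Power is above 99.99% at ρ = 0, 99.996% at ρ = 0.5 and 99.91% at ρ = 1.
- Three-scan average, e3 = 0: effect 0.67, SD 1.59 × √((1+2ρ)/3). Power is 99.7% at ρ = 0.3 and about 97% at ρ = 0.7.

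**Step 5. Repeat ablation.** A lesion made after the 3-month scan is absent from the first post-ablation scan and present on the second, so the definition counts it as new fibrosis. Bias = (difference in repeat rate) × (scar per repeat). Neither figure is in the documents. With an assumed 5 to 10 points of scar, each percentage point of difference in repeats adds 0.05 to 0.10 points. Reaching the half-width of 0.385 would take a difference of about 4 to 8 percentage points (0.385/0.10 to 0.385/0.05). Reaching the 2.0-point effect would take 20 to 40.

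**The case against.** The best defence is that the plan can be read coherently. The imaging sections describe a sequence: baseline for pre-existing fibrosis, 3 months for scar, 12 months for new enhancement against the 3-month scan. On that view the endpoint definition lists the scans the sequence uses, the *CMR Protocol* sentence is a general remark about imaging, and the model is a physician-clustered analysis of one 12-month value. Nothing would be averaged. This reading is available. But *Analysis of LA Fibrosis Progression* does not adopt it, and its wording about changes at three time points over follow-up points elsewhere. A decisive test should not depend on which reading the analyst prefers.

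Three other objections stand and limit the point.

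- **Units.** A reader might infer that the two denominators contradict each other. They describe different quantities, baseline fibrosis and new fibrosis. They conflict only if the modelled changes are computed across the two.
- **The factor of two.** A reader might infer that the plan halves the effect. That needs both a zero 3-month effect and a model in which the 3-month change is a response. The documents establish neither.
- **Repeat ablation.** A reader might infer a demonstrated bias. The mechanism follows from the definition, and Exclusion Criterion 14 recognises similar confounding at entry, but its size is unknown. The intention-to-treat set, "treating all randomized patients with available outcome data regardless of compliance", implies that such scans are analysed as they stand, which is a proper primary analysis. This supports no more than an optional sensitivity analysis.

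**Conclusion.** The point holds as a gap in specification that should be fixed. The endpoint and the sample size describe one 12-month value. The success rule uses a coefficient that, as written, may be that difference or an average over visits, and the reference scan is not settled. For a 12-month effect of 2.0 points, the two-change average estimates 1.0 to 2.0 as the assumed 3-month effect goes from 0 to 2.0. Under the single-value reading the gap is nil.

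It would be wrong to conclude that the fibrosis endpoint is underpowered. The plan's power reproduces. At SD 1.59, taken to apply to the 3-month change as well, power remains above 99.9% for the two-change average and about 97% to 99.7% for the three-scan average (correlation 0.7 to 0.3). On the plan's own inputs a significant result would be expected under any of these readings. What changes is the size and meaning of the reported effect.

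The covariate rule is also unsettled: one section plans Utah-stage adjustment outright, while two make adjustment depend on imbalance or confounding seen in the data.

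**What to change.** 1. Reconcile the endpoint definition, *CMR Protocol*, *Twelve-month CMR* and *Analysis of LA Fibrosis Progression*, with the units in *Baseline CMR* and *Twelve-month CMR*, to one variable, one reference scan and one denominator.
2. Make the decisive test the 12-month between-arm comparison of that variable. Adjust in advance for baseline left atrial fibrosis and the randomisation strata (age group and AF type), and keep the physician effect.
3. If percentage fibrosis at each scan is modelled instead, include visit and treatment-by-visit terms and name the 12-month treatment contrast as decisive.
4. Optional: report repeat-ablation counts by arm, and add one sensitivity analysis that sets 12-month scans taken after a repeat left atrial ablation to missing and imputes them. It relies on missing-at-random in patients selected by recurrence, so the as-scanned intention-to-treat analysis stays primary.

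The cost is SAP wording before database lock and a little more analysis. No new data are needed: the baseline scan and strata are already collected, repeat ablation is already a secondary endpoint, and *Definition of Trial Outcome using ECG Device* already uses its date.

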#### **D. Analysis of the secondary endpoints**

The secondary endpoints will be analyzed only as supporting evidence. There will be no intention to claim treatment benefits for the listed secondary endpoints. As such, data analysis for secondary endpoints are purely for descriptive purposes and not for drawing inferences.

#### *Statistical Analysis Software*

Statistical analysis will be performed using SAS version 9.4 and STATA version 14.

### **Food and Drug Administration (FDA) Approval**

---

The EDORA trial will be using an FDA approved device as well as the FDA approved drug dronedarone. The ECG Preventice monitoring device will transmit ECG recordings every 30-days onto its respective application on a paired mobile device. As dronedarone is already a marketed drug, we have received an FDA IND exempt status to proceed with this clinical trial.

**PIND Exempt No: 153638**

## **Study Training & Monitoring**

---

All enrolled sites will receive study protocol training via a site initiation visit (SIV). Prior to the SIV, all study staff should review and be familiar with the study protocol. In addition to study protocol training, the SIV will also cover use of the electronic data capture platform (DACIMA Software, Inc. Electronic Data Capture) and the Merisight Web Portal (for upload of CMR scans). Training for Montrium eTMF Connect and Preventice Cardiac Monitors web portal will be conducted via site self-review of vendor training material.

Following the SIV and site activation, all sites will be monitored via site monitoring visits (SMVs) per frequency specified in the clinical monitoring plan. As much as possible, all site monitoring will occur remotely via monitor access to the EDC, eTMF, and source document access as outlined in the clinical monitoring plan. To ensure contemporaneous data entry, all sites must enter data into the EDC within 3 business days. Sites are also responsible for responding to monitor queries in the EDC and/or eTMF within 5 business days. Prior to a SMV, the sites are to ensure that all study documentation is complete, up-to-date, and query-free. For additional information on site requirements, please refer to the clinical monitoring plan.

## **ClinicalTrials.gov Requirements**

---

The EDORA trial is registered at ClinicalTrials.gov in accordance with Federal Regulations.

**NCT: 04704050**

## **Study Records Access and Retention**

---

### *Electronic Data Capture Platform*

Tulane University ARO will use DACIMA Clinical Suite by Dacima Software Inc. as the centralized clinical database. The DACIMA Clinical Suite is compliant with good clinical practices and FDA 21 CFR Part 11 requirements. Only enrolled participants will be entered into the EDC and will be assigned a consecutive number (that includes the site's number) by the site's Research Coordinator. All changes made to the clinical data will be captured in an electronic audit trail available for review. Sites are also responsible for maintaining source documents in a physical subject's binder.

### *Electronic Trial Master File (e-TMF)*

Tulane University ARO will use eTMF Connect by Montrium as an electronic trial master file (eTMF). eTMF Connect uses a TMF reference model, which provides standardized taxonomy and reference for TMF content. Each trial site will be responsible for uploading regulatory documents on EDORA eTMF Connect.

### *Record Access*

All medical records and study source documents will be made available to authorized representatives at Tulane University ARO, upon request, for verification of study documentation. All medical information and data generated from this clinical trial will be made available for inspection upon request by representatives of Tulane University ARO and the Institutional Review Board (IRB) for each clinical trial site.

Page 37 of 49

Version 4.0:  
Revision Date: April 27th, 2022

Copyright© April 2022 Tulane University School of Medicine, Academic Research Organization on behalf of the Principal Investigator.  
All rights reserved.

TULANE UNIVERSITY  
Academic Research Organization

### *Retention of Records*

Records relating to the EDORA trial shall be retained for a period of 7 years after the completion of this clinical trial. Completion of this trial will be based on the planned analyses described in the protocol as well as completion of all publications relating to this clinical trial. All records shall be accessible for inspection and copying by authorized representatives of the regulatory authorities at reasonable times and in a reasonable manner [45 CFR §46.115(b)].

### **Schedule of Events**

---

PROCEDURES	SCREENING VISIT	BASELINE VISIT (DAY -90 TO 0)	DAY OF CARDIAC ABLATION (DAY 0)	3-MONTH VISIT (DAY 90±30)	6-MONTH VISIT/PHONE CALL (DAY 180±30)	9-MONTH VISIT/PHONE CALL (DAY 270±30)	12-MONTH VISIT (DAY 365±30)	13-MONTH PHONE CALL (END OF TRIAL) (DAY 365±30)
SIGNED ICF/ HIPAA FORM	X							
ASSESSMENT OF ELIGIBILITY CRITERIA								
REVIEW OF MEDICAL HISTORY	X							
HEIGHT, WEIGHT, VITAL SIGNS	X (Height measured here)	X	X	X			X	
ECG	X							
INCLUSION/ EXCLUSION CRITERIA	X							
TRIAL MEDICATION								
RANDOMIZE			X					
ABLATION			X					
DISPENSE TRIAL MEDICATION			X 3-month supply	X Some/9-month supply	X (Remaining supply)	X (Remaining supply)		
DRUG COMPLIANCE				X	X	X	X	
CONCOMITANT THERAPY	X	X		X	X	X	X	

---

 All events listed under a study timepoint may be asynchronous. However, all events must occur within that timepoint. For more guidance, please review protocol sections “**Study Procedure and Data Elements**”.

AE MONITORING			X	X	X	X	X	X
BLOOD DRAW		X		X			X	
RETURN OF TRIAL MEDICATION				X			X	
PHYSICAL AND MEDICAL EXAMINATION								
MEDICATION(S) REVIEW	X	X	X	X	X	X	X	X
REVIEW OF MEDICAL HISTORY		X	X	X	X	X	X	X
VITAL SIGNS		X	X	X			X	
PHYSICAL EXAM	X							
OTHER MEASURES								
CMR SCAN		X		X			X	
ECG MONITORING KIT (BodyGuardian® MINI Plus EL)			X	X	X	X	X	
AFEQT QUESTIONNAIRE		X		X			X	
AFSS QUESTIONNAIRE		X		X			X	

## Appendix A: Placebo Composition

Placebo Composition (Provided by Sanofi Pharmaceuticals)

Ingredients	Compendial grade	Function	Unit quantity mg/tablet
Core tablet			
Microcrystalline cellulose	NF/Ph.Eur.	Diluent - binder	266.0
Starch (corn) - Maize starch	NF/Ph.Eur.	Diluent - disintegrant	38.0
Crospovidone (type A)	NF/Ph.Eur.	Disintegrant	15.2
Colloidal silicon dioxide - Colloidal anhydrous silica	NF/Ph.Eur.	Flow agent aid	1.9
Lactose anhydrous (a)	NF/Ph.Eur.	Diluent - binder	435.1
Magnesium stearate (b)	NF/Ph.Eur.	Lubricant - antiadherent	3.8
Core mass :			760
Coating/Polishing			
Hydroxypropyl methylcellulose - Hypromellose	USP/Ph.Eur.	Film agent	7.25
Titanium dioxide (E171)	USP/Ph.Eur.	Opacifier	1.00
Polyethylene glycol 6000 - Macrogol 6000	NF/Ph.Eur.	Plasticizer	1.75
Purified water (c)	USP/Ph.Eur.	Coating solvent	(85.00)
Film-coating mass :			10
Carnauba wax	NF/Ph.Eur.	Polishing agent	(traces) 0.13
Film-coating mass :			770

(a)CEPs for BSE/TSE risk are provided in Appendix 3.1.A.2

(b)From vegetable origin

(c)Eliminated during the manufacturing process

## Appendix B: CMR Protocol

The sequences and measurement performed will be the following:

Page 40 of 49

Version 4.0:  
Revision Date: April 27th, 2022

Copyright© April 2022 Tulane University School of Medicine, Academic Research Organization on behalf of the Principal Investigator.  
All rights reserved.

TULANE UNIVERSITY  
Academic Research Organization

1. Cine of LV – stack of SA slices covering whole LV, 2-, 3-, and 4-chamber  
Assessment of LV function and strain  
LV function: Ejection fraction (%)  
LV strain: global longitudinal strain in % and strain rate in cm/s
2. Pre-Contrast T1 Mapping: 3 SA (base, middle, apex) slices  
Assessment of LV fibrosis (in %)
3. MR Angiography - ECG-gated, respiratory navigated  
Assessment of LA and LAA shape. Useful for LA wall segmentation
4. Cine of LA: stack of axial slices covering whole LA  
Assessment of LA function and strain

For LA function and shape assessment, a stack of contiguous axial cine images covering the whole LA will be obtained. Tissue-tracking approach will be used to quantify LA strain and phasic volumes from the cine images, a method described previously. This method has been previously validated with excellent reproducibility (intra-class correlation coefficients between 0.90 to 0.97 for LA volumes and strain). Endocardial and epicardial LA borders will be defined at end-systole by a blinded operator. Using defined borders in each view, the software will track the LA myocardium in subsequent frames. The operator will validate the generated contours during the cardiac cycle for quality control. Images with poor tracking will be excluded. In each frame, the LA volume will be calculated. Maximum, minimum, and pre-atrial contraction LA volumes in cm (LAVmax, LAVmin, VPreA) will be extracted from volume curve. The point on the LA volume curve during diastole just before the fast descent following a period of stability in LA volume will be defined as pre-atrial contraction volume. At that point, the atrial strain rate is equal to zero. All measured volumes will be indexed to body surface area. LA sphericity index (LASI) will be calculated from LA endocardial shell segmented from CE-MRA and 3D LGE scans. The global longitudinal strain (in % (of shortening)) and strain rate (in cm/s) will be calculated by averaging all of the strain values obtained. Smax and SpreA will be identified from the strain curve.

LA function measurements (global emptying fraction, active and passive function) will be based on LA minimal, maximal, and pre-atrial kick volumes.

$$\begin{aligned}\text{Total LA EF (in \%)} &= [(LAV_{\text{max}} - LAV_{\text{min}})/LAV_{\text{max}}] \times 100 \\ \text{Active LAEF (in \%)} &= [(V_{\text{PreA}} - LAV_{\text{min}})/V_{\text{PreA}}] \times 100 \\ \text{Passive LAEF (in \%)} &= [LAV_{\text{max}} - V_{\text{PreA}}]/LAV_{\text{max}}] \times 100\end{aligned}$$

5. Post Contrast T1 Mapping: 3 SA (base, middle, apex) slices  
Assessment of LV fibrosis (in %)
6. TI-Scout
7. 3D LGE of LA  
Assessment of LA fibrosis (in %)

